9. RESEARCH METHODS

9.1 STUDY DESIGN

This is a multi-center, non-interventional (observational) cohort study based mainly on newly collected data.

In 20 Italian Pulmonary Centres about 400 consecutive COPD patients will be enrolled in approximately 8 months (from first patient enrolled). Patients will be followed up for 1 year, with an intermediate evaluation after 6 (+/-1) months from baseline (which is compatible with current clinical practice in Italy for COPD patients management).

No treatment will be administered to the patients on the protocol basis, since this is a non-interventional study and the assessment and treatment of the enrolled patients will be applied according to standard clinical practice. The patients switching or stopping treatment during observation period will not be withdrawn from the study. Few patients are expected to stop treatment during study; if any, for primary objective evaluation they will be censored at the latest available visit.

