9.5 STUDY SIZE

The sample size was determined on the basis of feasibility criteria. In fact, according to the volume of patients managed by the centres involved in this study, inclusion of 400 subjects (20 patients/center) with the characteristics defined at Inclusion/Exclusion criteria paragraphs is deemed reasonable for the planned enrolment period (8 months). Assuming a drop-out rate ranging from of 5% to 20% (including not evaluable,lost-to follow up and not on treatment patients), effective sample size is expected to range between 320 (drop out=20%) and 380 (drop out=5%).

An evaluation of the possible achievable precision of the estimates was performed considering the primary objective of the study. No data on treatment satisfaction is available about COPD patients specifically, therefore available literature data was used as a reference to evaluate possible scenarios. In particular, literature data about TSQM was found on multiple sclerosis, psoriasis, etc, showing the global satisfaction mean score ranging from 54.4 to 79.7 (17,18)].

Table 2 shows the 95% confidence interval half-width and standard error (SE) of the expected mean of global satisfaction score under different sample sizes.

| | | | | |
|------------------------------------|-------------|-------|-------------|-------|
| Expected Mean (SD) | 54.4 (21.4) | | 79.7 (16.6) | |
| Sample Size | 380 | 320 | 380 | 320 |
| 95% confidence interval half width | 2.152 | 2.345 | 1.669 | 1.819 |
| Standard error (SE) | 1.098 | 1.196 | 0.852 | 0.928 |

Table 2. 95% confidence interval (CI) half-width and standard error (SE) of the expected mean assuming N=380/320 evaluable patients [19]

In all considered scenarios the relative error of the estimate (CI half-width/expected mean) is lower than 30%. The lower the sample size and the higher the standard deviation, the lower the estimate precision.

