The patients switching treatment during observation period will not be excluded from analysis and will be evaluated at each visit as above described. Few patients are expected to stop treatment during study; if any, for primary objective evaluation they will be censored at the latest available visit. Comparisons of satisfaction between different treatment/devices are not matter of this study, throughout all analysis treatments will be lumped together.

Secondary objectives

#1 To describe patient disease perception (B-IPQ), adherence to COPD treatment (MMAS4), health status (CAT) and dyspnea (MMRC) during a 12-month observation period

A description of B-IPQ (consequences, timeline, personal control, treatment control, identity, concern, emotions and illness comprehensibility), MMAS-4, CAT and MMRC scores will be provided at baseline and at follow-up visits. Scale scores will be summarized at each time point. Patients lost to follow up will be considered until their last available visit. Missing items of questionnaires/scales will be replaced if applicable according to scoring algorithm [32-38].

#2 To analyse the relation between treatment satisfaction for medical treatment and demographic/clinical parameters and PROs during a 12-month observation period

Three regression models (one for each TSQM-9 domain score) will be estimated; the dependent variable will be domain score and the independent ones will be: age and gender (at enrollment), number of exacerbations, relevant spirometry parameters (such as FEV1, FVC, FEV1 % of the predicted, RV, TLC, DLCO), level of dyspnea (MMRC score), impact of COPD on a patient's life (CAT) and treatment adherence (MMAS-4 score) collected during observational period. Because dependent variable will be collected at each study visit, repeated measures models will be estimated taking into account all available values for dependent and independent variables. Patients could be classified in mild or moderate/severe according to lung function parameters. This will allow to evaluate treatment satisfaction in different groups of patients.

The patients switching treatment during observation period will not be excluded from analysis and will be evaluated at each visit. The patients stopping treatment during study will be censored at last available visit.

#3 To describe the health care resources utilization and related cost during a 12-month observation period

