Non-parametric bootstrap method will be applied to cost data for calculating 95% confidence intervals (22-23).

A multiple linear regression model will be performed to investigate statistical significance of INHS cost predictors (24).

#4 To assess the correlation between patients' satisfaction and resource utilization.

Correlation indexes will be calculated between treatment satisfaction domain scores of TSQM-9 and healthcare resource consumption (such as number of hospitalizations, emergency room accesses, GP visits, laboratory test. etc... during observation period) at 12-month follow-up visit. The patients switching treatment during observation period will not be excluded from analysis and will be evaluated at each visit. The patients stopping treatment during study will be censored at their last available visit.

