4.3 Patients' satisfaction for medical treatment (TSQM-9) (primary objective)

Table 10. Patients' satisfaction for medical treatment (TSQM-9 items) at each study visit

The table will provide absolute and relative frequency of patients' answers to TSQM-9 items (see Appendix 8.3) at each study visit.

Percentages will be calculated over the number of patients respectively evaluable at the time point considered, namely at enrollment (i.e. FAS patients), at 6 months (i.e. evaluable patients at 6 months) and at 12 months (i.e. evaluable patients at 12 months).

Table 11. Patients' satisfaction for medical treatment (TSQM-9 subscales) at each study visit

The table will provide the descriptive statistics (mean, median, standard deviation, quartiles, min, max) of the TSQM-9 subscales scores (as defined in "Computed variables" chapter) at each study visit.

Changes from enrollment in TSQM-9 subscales scores (see 'Computed variables' chapter) will be also summarized by visit.

95% confidence intervals limits of the mean will be provided for each estimate (i.e. TSQM-9 subscales scores and changes). Descriptives will be calculated over the number of patients respectively evaluable at the time point considered, namely at enrollment (i.e. FAS patients), at 6 months (i.e. evaluable patients at 6 months) and at 12 months (i.e. evaluable patients at 12 months).

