Table 17. Relation between treatment satisfaction and demographic/clinical parameters and PROs during 12 month observation period (Repeated measures regression models) – Effectiveness domain

A regression model will be estimated; the dependent variable will be the effectiveness domain score of TSQM-9 and the independent ones will be the following:

- age and gender at enrollment;
- number of exacerbations at enrollment;
- relevant spirometry parameters at enrollment (a selection of the following parameter will be done, based on data availability: FEV1, FVC, FEV1 % of the predicted, RV, TLC, DLCO);
- patient's disease severity in terms of level of dyspnea (mMRC score) or CAT total score (depending on data availability) at enrollment (since they are expected to be intercorrelated measures, as reported by 2017 GOLD guidelines, only one of such measures will be considered in the model);
- MMAS-4 score at enrollment.

Center will be included as random effect and study visit (visit1/enrollment, visit2/6months, and visit3/12months) as timepoint.

During data elaboration, the Biostatistician will assess the intercorrelation between the proposed variables, in order to evaluate the opportunity to exclude some of the listed independent variables that are highly associated to each other; in case of important lack of data for certain parameters, such parameters may be excluded as well from the final model.

Because measures referred to the dependent variable will be collected at each study visit, a mixed model for repeated measures will be estimated; moreover, interaction terms between independent variables will be evaluated and, if not significant, they will not be included in the final model. The optimal covariance structure will be evaluated during analysis (preferably "first-order autoregressive correlation" or "unstructured" options). A stepwise selection method will be evaluated during the analysis in order to identify the variables to be included in the final model.

The patients switching treatment during observation period will not be excluded from analysis. The patients stopping treatment during study will be censored at last available visit.

The analysis will be performed considering only evaluable patients at 12 months.

Table 18. Relation between treatment satisfaction and demographic/clinical parameters and PROs during 12 month observation period (Repeated measures regression models) – Convenience domain

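### The protocol censors patients who stop treatment in the primary analysis, but the SAP's primary tables carry no such rule, so scores given after stopping can enter them

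*Protocol*

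**What the plan says.** **Protocol**
- 9.1 keeps these patients under observation: "The patients switching or stopping treatment during observation period will not be withdrawn from the study". They can therefore return and complete the TSQM-9.
- 9.7, primary objective: "Few patients are expected to stop treatment during study", and if any do, "for primary objective evaluation they will be censored at the latest available visit". Patients who switch are instead assessed at every visit.
- 9.7 states the same rule for objective #2 and for objective #4 ("The patients stopping treatment during study will be censored at their last available visit").
- 9.5 takes the effective sample size after a drop-out of 5% to 20%, "including not evaluable,lost-to follow up and not on treatment patients".

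**SAP**
- 2.2 and 2.3 define the 6- and 12-month evaluable sets by Full Analysis Set membership, an in-window visit and at least one computable TSQM-9 domain score. The footnote to Chart 1 adds only that the score be computable.
- 4.3, for primary Table 11: "Descriptives will be calculated over the number of patients respectively evaluable at the time point considered". Table 10 uses the same denominators.
- 4.9, for Table 17, carried to Tables 18 and 19 by cross-reference: "The patients stopping treatment during study will be censored at last available visit".
- 4.11, for Table 37, correlates 12-month TSQM-9 scores with resource use and does not mention patients who stop.

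**The concern.** The censoring rule belongs to the primary objective in the protocol, yet in the SAP it appears only for one secondary objective. A programmer who follows the SAP would summarise every TSQM-9 score from an in-window visit, including satisfaction with a drug the patient no longer takes. The same scores would be handled one way in Tables 17-19 and another way in Tables 10, 11 and 37.

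The planned checks would not catch this. SAP section 6 verifies evaluability and the Table 11 scores against the SAP's own algorithms, so an uncensored Table 11 would pass.

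At stake are the visit means of the primary endpoint, their changes from enrolment and the objective #4 correlations.

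**Working it through.** **1. Is treatment status tested anywhere else in the SAP?** Inclusion criterion 4 (SAP 2.1) looks at treatment at enrolment and admits therapies that end later. Criteria 11-13 and 14-16 cover data collection, visit window and TSQM-9 completeness only. Nothing in the visible text tests treatment status after enrolment for Tables 10, 11 or 37.

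**2. Is the omission declared?** SAP 4.9 openly declares one departure from protocol 9.7, the decision to use no post-baseline covariates. There is no such statement about censoring in 4.3 or 4.11, and the revision history (section 7) names none.

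**3. Can a patient who has stopped supply a score?** Yes. Such patients stay in the study (protocol 9.1), and the TSQM-9 instructions in SAP Appendix 8.3 allow answers that refer back to the last use of the drug.

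**4. Do the supportive tables isolate these patients?** No. Tables 45 and 46 compare switchers with non-switchers. SAP section 3 says in words that stopping a COPD treatment is a switch. Its record count, however, needs more than one COPD record that is either ongoing at the end of observation or started after enrolment. A patient who stops a single baseline drug has no such record and would count as a non-switcher.

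**5. The plan's own precision figures.** Inputs from protocol 9.5: 400 patients, drop-out of 5% or 20%, SD 21.4 or 16.6.
- n = 400 × 0.95 = 380; n = 400 × 0.80 = 320.
- Half-width = 1.96 × SD/√n.
- SD 21.4: 2.152 (n = 380) and 2.345 (n = 320).
- SD 16.6: 1.669 (n = 380) and 1.819 (n = 320).

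All four agree with the protocol's Table 2.

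**6. Size of a possible shift.** Let f be the share of analysed patients who are off treatment at a visit, and D the mean score gap between on- and off-treatment patients. The visit mean shifts by f × D. The documents give neither input, so both are assumptions.

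| f | D = 10 | D = 20 | D = 30 |
|---|---|---|---|
| 1% | 0.1 | 0.2 | 0.3 |
| 2% | 0.2 | 0.4 | 0.6 |
| 5% | 0.5 | 1.0 | 1.5 |
| 10% | 1.0 | 2.0 | 3.0 |

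The shift equals a planned half-width when f = half-width/D. For D = 20 this is 1.669/20 = 8.3% to 2.345/20 = 11.7%. For D = 10 it is 16.7% to 23.5%, and for D = 30 it is 5.6% to 7.8%.

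**The case against.** The strongest reply is that the protocol's phrase is undefined. Censoring at the latest available visit could mean the last visit attended. Nearly the same words are used in 9.7 for patients lost to follow-up, where they only mean using whatever visits exist. On that reading the SAP's visit-wise tables already comply. The rule in SAP 4.9 would also remove nothing, because that analysis is limited to patients evaluable at 12 months.

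The ambiguity is real and needs settling, but this reading leaves the rule empty. Protocol 9.7 sets patients who stop against those who switch and are assessed at every visit, and 9.5 treats off-treatment patients as lost to the effective sample. The 9.5 wording is a planning assumption rather than an analysis rule, so it supports the point without deciding it.

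Other parts of the reply stand:
- A reader might infer that off-treatment scores do enter the primary result. The documents show only that they can. A patient must stop, return within the window and complete all three items of a domain.
- A reader might infer that the primary result is materially biased. The protocol expects few such patients. An off-treatment share of 5-10% among those still giving scores would match or exceed the lower drop-out allowance of 5%, or use a quarter to a half of the upper one of 20%, and that allowance also covers lost and non-evaluable patients. The 20-point gap has no source in the documents.
- A reader might infer that the SAP deliberately reverses the protocol. It is silent, not contrary.
- Censoring on therapy end dates alone would be wrong. The end of one drug often marks a switch, and the protocol keeps patients who switch.
- The text of SAP 4.14 and the section 5 layouts are not visible, so a footnote there cannot be excluded.

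**Conclusion.** The mismatch holds. The protocol states a censoring rule for the primary objective and for objectives #2 and #4. The SAP carries it only into the objective #2 models and declares no departure. Followed as written, the SAP can place post-stopping scores in Tables 10, 11 and 37.

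The effect cannot be sized from the documents. If the expectation of few stoppers holds, say 1-2% with a gap of 10-30 points, the visit mean moves by 0.1 to 0.6 points, well inside every planned half-width. At 5-10% and 20 points it moves by 1.0 to 2.0, and the upper end exceeds the narrower half-widths (1.669 and 1.819) but not the wider ones (2.152 and 2.345). The conclusion rests on reading the censoring visit as the last one before stopping, which is the only reading that gives the rule any content.

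This should be corrected in the SAP. It is not evidence that the primary result is wrong.

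**What to change.** Reconcile protocol 9.7 (primary objective, #2 and #4) with SAP section 3 (switch definition), 4.3, 4.9 and 4.11. In the SAP:

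1. Define an analysis flag for stopping all COPD treatment. Derive it from therapy start dates, end dates and ongoing flags across all of a patient's COPD records, and keep it distinct from a switch and from ending one of several drugs.
2. Define the censoring visit as the last visit before stopping, or declare and justify a departure from the protocol in the way 4.9 does for the covariates.
3. Apply the same rule to Tables 10 and 11 (4.3), Tables 17-19 (4.9) and Table 37 (4.11). State whether a censored score still counts towards evaluability criteria 13 and 16.
4. Report the number of stoppers and of censored scores at each visit.
5. Show the all-scores version as a sensitivity analysis.

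Cost: one derived flag from dates already collected, SAP wording, and one extra set of rows or one extra column. No new data are needed.

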Literature data in Italian real world setting about the relation between treatment satisfaction and clinical parameters and PRO are lacking. In a general population survey conducted in ten countries of the Middle East and North Africa region, together with Pakistan on COPD subjects with respiratory symptoms the treatment satisfaction was relatively high, with 83.2% of respondents somewhat or very satisfied with their physician's management. Treatment satisfaction was associated with not having exacerbations and with knowledge, subjects who claimed to be more informed being more satisfied with their management (37). Chronic obstructive pulmonary disease is a major cause of chronic morbidity and mortality worldwide, and its epidemiological, clinical, and socioeconomic impact is progressively increasing. A first estimate of the economic burden of COPD in Italy was conducted in 2008 (the SIRIO [Social Impact of Respiratory Integrated Outcomes] study) (40). Average direct costs and total societal costs in the year before enrollment were €2,932 and €3,291, respectively. Direct cost was €2,461 (hospitalization: €1,570; outpatient: €344; and pharmaceutical: €547) in the first year of follow-up, while total societal cost was €2,707. The therapeutic approach followed in a specialist center, based on the application of clinical guidelines, has been shown to be a highly effective investment for the long-term management of COPD. A small increase of pharmaceutical costs per year allowed a substantial saving in terms of hospitalizations, costs related to outpatient services, and indirect costs.

Patients with COPD are at increased risk for lung infections and other pathologies (eg, pneumonia). A study on two cohorts of 84130 COPD patients each, showed that COPD patients with newly developed pneumonia have higher health care resource utilization and/or costs in all areas explored: hospitalizations, outpatient visits, ER visits, and prescription costs (38). In this study, the pneumonia cohort was approximately nine times more likely to have a hospitalization and four times more likely to have an ER visit during the 12 months of follow-up. A total cost savings of \$22348 was estimated to be associated with the prevention of pneumonia based on the sum of the mean differences of \$14353 in inpatient costs, \$6891 in outpatient costs, and \$1104 in pharmacy costs between the pneumonia and control cohorts.

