The health care resources consumption will take into consideration the following events related to management of COPD and COPD exacerbations: inpatients and outpatients hospitalization (inward and day-hospital), accesses to emergency room, General Practitioner (GP) and outpatient visits, laboratory tests and examinations, pharmacological (LABA, LAMA, SABA, SAMA, ICS/LABA, steroids, antibiotics, long-Term Oxygen Therapy, etc.) and non-pharmacological therapies (pulmonary rehabilitation) occurred/administered during study period.

Medications for adverse events will be considered too.

The annual direct health care resource consumption and related cost will be provided by means of descriptive statistics of the variables mentioned above. In order to describe the health care cost from enrolment up to the end of 12-month follow-up according to the INHS point of view (26), a two steps approach will be followed: (i) first of all the resource consumed since enrolment will be calculated and then (ii) a monetary value will be assigned to the resource consumption.

(i) Health care resources consumption exclusively related to COPD, COPD exacerbations and COPD-drug-related adverse events will be computed during observational period in terms of pharmacological and non-pharmacological treatments, number of (inward and day-hospital) hospitalizations, number of emergency room accesses, number of GP visits, specialist visits, laboratory tests or examinations (spirometry, FEV1, FVC, FEV1 % of the predicted, RV, IC, TLC, DLCO).

(ii) In order to estimate the economic impact on health care sector related cost (30) of the above mentioned health services (hospital admissions, visits, treatments, examinations, spirometry) consumption, a monetary value to each event recorded will be assigned, as defined by the Italian Ministry of Health through the tariffs in force for outpatient setting (31). The cost of hospitalization will be valued according to the most recent available diagnosis-related group (DRG) tariffs (32); finally, pharmacological treatments will be costed at consumer price. All costs will be expressed in €2015. A monthly (or yearly) cost will be provided by taking into account patients according to duration of observation and parametrizing each patient to the 12-month observation period.

Descriptive statistics (mean, standard deviation, median, minimum and maximum) of the annual direct health care resource consumption and related cost will be provided.

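### The cost-predictor regression names no variance estimator; read as model-based least squares, its standard errors can be too small or too large when a predictor affects cost and its groups differ in size

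*Protocol*

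**What the plan says.** Protocol section 9.7, objective #3, describes how resource use is priced and then scaled to a year of follow-up ("A monthly (or yearly) cost will be provided by taking into account patients according to duration of observation and parametrizing each patient to the 12-month"). For the cost summaries it states: "Non-parametric bootstrap method will be applied to cost data for calculating 95% confidence intervals". The next sentence is the regression: "A multiple linear regression model will be performed to investigate statistical significance of INHS cost predictors (24". Nothing there gives a variance estimator, a transformation, a link function or a list of predictors. The corresponding part of the protocol abstract stops at the bootstrap and does not mention a cost regression.

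The SAP repeats cost within secondary objective 3 (section 1) and in Chart 1 (full analysis set). Section 4.10 (Tables 20–36) covers resource use only, and the list of tables in section 5 (Tables 1–46) has no cost table. Where the SAP departs from protocol 9.7 for objective #2, section 4.9 says so. No such statement withdraws the cost regression, and the revision history does not mention it. The protocol sentence is therefore the only instruction for this analysis.

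**The concern.** The plan uses a distribution-free method to describe cost, and then tests predictors of the same cost with a model whose default standard errors assume equal variance. Equal variance is doubtful here. The protocol's background cites Italian figures: "Direct cost was €2,461 (hospitalization: €1,570; outpatient: €344; and pharmaceutical: €547) in the first year of follow-up". If hospital care is most of the cost, total cost depends mainly on whether a patient is admitted, and a predictor of admission changes the variance along with the mean. Scaling short observation periods up to 12 months may add more unequal variance; that effect has not been quantified.

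At stake are the intervals and p-values attached to cost predictors. They could look more precise than they are for a small high-cost group, or less precise for a large one.

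**Working it through.** **Inputs from the documents.** The cost components add up: 1,570 + 344 + 547 = 2,461 euro. Hospital share: 1,570/2,461 = 63.8%. Non-hospital cost: 344 + 547 = 891 euro. Evaluable patients (protocol 9.5): 400 × 0.80 = 320 to 400 × 0.95 = 380. The documents give no figure for the cost regression to reproduce; Table 2 of the protocol concerns the satisfaction score only.

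**Assumed inputs.** 20% of patients admitted, so the mean cost per admitted patient is 1,570/0.20 = 7,850 euro. The predictor is binary with prevalence p, and its admission risks average about 20%, for example 0.2 × 0.45 + 0.8 × 0.14 = 0.202.

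**Why the direction depends on group size.** Let group 1 (share p) have cost variance v1 and group 0 have v0. The true variance of the mean difference is v1/(np) + v0/(n(1−p)). Least squares pools the variances, and in large samples its estimate is v1/(n(1−p)) + v0/(np), so the group sizes are swapped. Hence

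(model SE / true SE)² = [p·v1 + (1−p)·v0] / [(1−p)·v1 + p·v0].

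This equals 1 if p = 0.5 or v1 = v0. It is below 1 if the more variable group is the minority and above 1 if it is the majority. Approximate coverage is 2Φ(1.96 × SE ratio) − 1.

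**Hand check, fixed cost per admission.** Hospital cost only: v is proportional to π(1−π), where π is the admission risk.

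| p | Admission risk | v1, v0 | Ratio² | SE ratio | Coverage |
|---|---|---|---|---|---|
| 0.2 | 45% v 14% | 0.2475, 0.1204 | 0.1458/0.2221 = 0.657 | 0.81 | 89% |
| 0.2 | 30% v 17.5% | 0.2100, 0.1444 | 0.1575/0.1969 = 0.800 | 0.89 | 92% |
| 0.8 | 23% v 8% | 0.1771, 0.0736 | 0.1564/0.0943 = 1.659 | 1.29 | 99% |

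Simulation with a fixed cost per admission gave 90% and 92% for the first two rows.

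**Hand check, variable cost per admission.** If the cost of an admission has a coefficient of variation of 1 (assumed), v is proportional to 2π − π². For p = 0.2 and 45% v 14%: v1 = 0.6975, v0 = 0.2604, ratio² = 0.3478/0.6101 = 0.570, SE ratio 0.755, coverage 86%.

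**Simulation** (gamma costs, predictor plus age, 4,000 data sets per row; SEs in euro):

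| Prevalence | n | Mean model SE / true SD | Ratio | Coverage |
|---|---|---|---|---|
| 20% | 320 | 574/752 | 0.76 | 86.2% (HC3 93.9%) |
| 20% | 380 | 526/707 | 0.74 | 85.2% (HC3 93.4%) |
| 10% | 320 | 776/1087 | 0.71 | 84.6% |
| 10% | 380 | 714/974 | 0.73 | 85.8% |
| 30% | 320 | 499/607 | 0.82 | 89.2% |
| 30% | 380 | 458/561 | 0.82 | 89.2% |
| 50% | 320, 380 | – | – | 94.7%, 95.3% |
| No effect | 320, 380 | – | – | 95.0%, 94.7% |

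Further runs at n = 350:
- Strong effect, minority predictor: least squares 85–90%, HC3 90–95%, bootstrap of whole patients 90–94%.
- Moderate effect (30% v 17.5%, prevalence 20%): least squares 91%, HC3 about 91–93%.
- High-cost majority (prevalence 80%, 23% v 8%): SE 27–29% too large, coverage 98–98.5%.
- Null covariate correlated with a real predictor: least squares rejects in 4–7% of runs.

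**The case against.** **The protocol never says that the standard errors are the default ones.** This stands. It names no estimator, and the bootstrap sentence is not expressly limited to means. The citation does not settle it. Reference 24 in the list is a quality-of-life instrument paper. The tariff citations in the same section run one number ahead of the list, so an Italian cost-of-illness study at reference 23 may be meant, and its method cannot be seen from here. The defect is an omission whose default reading is problematic.

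**A reader might infer that false-positive findings are inflated.** The documents do not support this. Section 9.7 promises a significance test, and a predictor unrelated to cost leaves the variance unchanged under the admission mechanism, so the test keeps about its 5% level. Rejection rates of about 8% to 46% can be produced by assuming a zero slope while the variance alone rises with the predictor, but nothing in the documents points to that pattern.

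**A reader might also infer that rising variance alone makes the standard errors too small.** It does not: a balanced predictor is fine, and a high-cost majority reverses the error.

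**The stakes are limited.** This also stands. The objective is descriptive, the regression is missing from the abstract, and the SAP has no cost analysis. The cited cost split comes from another cohort, whereas this study enrols only patients without an exacerbation in the last 3 months. At a moderate effect the gain from robust inference is small.

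**Conclusion.** The concern holds as a conditional one. Read as model-based least squares, the planned regression gives standard errors and p-values that can be wrong in either direction when a predictor affects cost and its groups are unequal in size. For a high-cost minority, coverage is roughly 85–91% with gamma costs and about 90% with a fixed cost per admission, against a nominal 95%. For a high-cost majority it is about 98%, so real effects may be missed. For balanced or null predictors it is about right.

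The direction follows from the variance formula. The size rests on assumed admission rates, effect sizes and cost distributions, because the documents give no cost SD, admission rate or predictor list. This is a cheap improvement to a secondary analysis and does not touch the primary objective.

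**What to change.** In protocol 9.7, objective #3, keep the linear mean model so that coefficients stay in euro. Add that confidence intervals and p-values for the coefficients come from heteroscedasticity-robust (HC3) standard errors, or from the planned non-parametric bootstrap with whole patients resampled. Name one of the two in advance and list the predictors. Carry this into SAP section 4.10 with a cost table, since the SAP lists cost under objective 3 without specifying an analysis. A gamma model with log link is an optional sensitivity analysis.

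The change needs one sentence and a few lines of code, plus the missing SAP entry. Some intervals will be wider. With strong skew or a rare predictor, coverage improves but may stay near 90%, and the report should say so.
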